## **2.2. Diseases under study**

For the current study we will focus on patients who present to the pneumonology, check-ups and infectious diseases outpatient clinic at the Clínica Universidad de Navarra with cough. This includes patients with cough of unknown origin and those with a previously diagnosed respiratory disease. As a symptom, cough: (i) represents an important reason for consultation at the clinic, (ii) represents a diagnostic challenge, and (iii) is an indicator of the efficacy of specific treatments for underlying respiratory conditions.

Examples of these conditions include, but are not limited to:

- **Chronic cough:** Typically considered to be any cough that lasts for 8 weeks or longer. This condition is thought to affect around 10% of the world adult population and can be caused by a myriad of different conditions, including: allergies, sinus infection, asthma, chronic obstructive pulmonary disease (COPD), cancer, gastroesophageal reflux disease (GERD), among others. (Song et al, 2016).

Its diagnostic process is typically lengthy, and largely based on empiric observations of response to different treatment schemes, which is in turn dependent on subjective reports from patients. Designing a method to objectively monitor this process will likely speed up diagnosis and lead to improved clinical outcomes and reduced costs in the healthcare sector.

- **Tuberculosis:** *Mycobacterium tuberculosis* is the leading infectious cause of death in the world, with most cases occurring in low-income countries. Global prevalence is unknown, but 25-47%

of the total population of India, China, the Philippines, and Pakistan (the five countries with the highest burden) are estimated to be infected (Ragonnet, Trauer, Geard, 2019). Chronic cough is a symptom of pulmonary tuberculosis, and a major driver for transmission of the disease (Turner, 2019).

- **Non-tuberculous mycobacterial infection (NTM):** Infections caused by mycobacteria other than the *M. tuberculosis* complex. NTMs are a common cause of chronic cough among patients with an underlying anatomical airway abnormality, and prevalence has steadily increased in the last decades, following improvements in diagnostic methods and increased incidence of iatrogenic immunosuppression for various rheumatologic and oncologic conditions, for example. Treatment schemes are often long and associated to poor patient adherence. Mortality rates among people with NTM are more than twice as high as those compared to the general population. (Wassilew, Hoffman, Andrejak, 2016. Park, Kan, Han, et al, 2019).
- **Asthma:** Over 339 million people was estimated to have asthma in 2016, making it once of the most important non-communicable diseases in the world. Cough, wheezing, and shortness of breath are typical symptoms. Although relatively simple, treatment with inhaled corticosteroids requires regular follow ups and monitoring based on subjective, self-reported indicators. (WHO, 2018).

### ***2.3. Evaluation of benefit/risk ratio for the participants in the clinical trial***

Privacy concerns have been addressed by the research team. All data and metadata collected by Hyfe are secured and stored in safe, GDPR-compliant servers. Only anonymized data is shared between the sponsor and co-investigators. There are no anticipated benefits for taking part in this study. Cough records will be used to enrich Hyfe's database and help evaluate its potential as a screening diagnosis tool for respiratory diseases.

### **3. OBJECTIVES OF THE TRIAL**

#### **Primary objective:**

1. To evaluate the value of AI-enabled cough monitoring systems for screening, diagnosis, and management of respiratory diseases in clinical practice.

#### **Secondary objectives:**

1. To assess the clinical performance of questionnaire-based clinical cough assessment by comparing cough records generated by Hyfe Cough Tracker™ to self-reported cough scores.
2. To generate databases of cough sounds annotated with demographic and medical data.
3. To determine the sensitivity and specificity of Hyfe Cough Tracker to detect and classify coughs in a controlled environment.
4. To determine the sensitivity and specificity of Hyfe Cough Tracker and Hyfe Air in a real-life setting.

Research questions to be addressed by this project include: (i) Is there a difference in the self-reported cough frequency of participants and that registered with acoustic surveillance systems? And (ii) can acoustic cough patterns facilitate the etiologic diagnosis of patients with chronic cough?

## **4. DESIGN OF TRIAL**

### **4.1. Global design**

This is a single center study to be carried out at the two campuses of the Clínica Universidad de Navarra, in the cities of Pamplona, and Madrid, Spain.

For the cough-monitoring process, we will use, an Artificial-Intelligence system (AI) that detects and records explosive putative cough sounds and identifies human cough based on acoustic characteristics (see below).

Potential participants either attending the outpatient clinic or hospitalized with a complaint of cough will be invited by their treating physician, or a member of the research team and included in the study by part of the research team. A researcher will instruct participants on how to install and use Hyfe Cough Tracker in their smartphones. If necessary, the researcher might provide participants with a smartphone configured to exclusively run Hyfe Cough Tracker™. Researchers who enroll participants will also be responsible of obtaining informed consent forms personally.

Once turned on, the app will monitor cough. Participants provided with a study phone will be instructed to run the app continuously and keep the study smartphone close to them for the period of monitoring.

Depending on the objective, participants will either be submitted to diagnostic procedures deemed necessary by their attending physician or will receive the treatment recommended by their attending physicians and will be monitored for a variable period.

#### **Monitoring period**

The monitoring period will vary for outpatient and inpatient participants. Inpatients will be monitored from the moment of first consultation/admission to the hospital until their discharge. Outpatients will be monitored for an initial period of one month, subject to modification

depending on the characteristics of specific diseases under study, and prior obtention of informed consent.

### **Assessment of correlation with self-reported questionnaires**

Participants will be asked to complete a daily online, standardized 100mm cough visual analogue scale (VAS), as described by Boulet et al in 2015. Participants will also be instructed to fill a validated Spanish version of the Leicester Cough Questionnaire (LCQ) (Muñoz et al, 2016) at the time of recruitment, and again at the end of the monitoring period.

These records will be compared with those registered by the cough surveillance system. We will evaluate the correlation between the mean weekly VAS score and the registered cough frequency.

### **Generation of annotated cough datasets**

Participants with an etiologic diagnosis at the time of enrollment, or in which it is reached before the end of the monitoring period, will be retrospectively included in disease-annotated datasets, to assess differences in the acoustic patterns of specific diseases with the neural network created by Hyfe.

### **Validation of Hyfe's technical performance**

A subgroup of participants and/or a group recruited outside the clinical setting will provide consent to participate in this sub-study by marking the sub-study box in the consent form.

Participants will remain for approximately 30 minutes in a quiet room. A smartphone connected to a lapel microphone will be placed at approximately 50 cm from the participant's mouth, another smartphone of the same model, not connected to an external microphone will be placed next to the first one. Each participant will also wear a lapel microphone connected to an audio recorder.

Participants will be instructed via a computer monitor to generate a series of voluntary sounds including but not limited to: reading a text, coughing, counting, sneezing and similar common sounds. There will be silent pauses between the elicited sounds. All sounds throughout this period will be recorded. Any accidental conversation will be deleted. The final audio will be stored in a database, coded with the participant's ID, sex, and age.

The cough counts registered by the two smartphones will be compared to the consensus evaluation of two medically trained researchers, who will be instructed to determine whether individual sounds were coughs or not.

Finally, the experiment will be repeated, playing back the records obtained from participants using a desktop speaker located at 50 cm of the two smartphones, to compare the application's performance detecting live vs recorded coughs. Audio will be played at decibels matching the average intensity of human coughs (Doherty et al, 1997).

A second sub-group of at least 24 participants will be instructed to use Hyfe continuously for a period between 6 and 24 hours, while they record themselves using a MP3 recorder connected to a lapel microphone. For this, participants will be provided with a smartphone exclusively destined to run Hyfe Cough Tracker, while simultaneously wearing the Hyfe Air wearable system. MP3 records will be processed and manually reviewed by two specially trained healthcare providers to count the number of coughs recorded. This data will be used to evaluate the performance of both devices compared to human listeners in a real-life scenario.

A patient (or their family or legal representative) may interrupt their participation in the study at any time and for whatever reason. The principal investigator may also withdraw a patient from the study if he considers that it is in the best interest of the patient.

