The validation parameters for the application will be calculated in the following way: Sensitivity = True positives (TP)/True positives (TP) + False negatives (FN), Specificity = True negatives (TN)/True negatives (TN)+ False positives (FP). PPV= TP/TP+FP, NPV= TN/TN+FN.

Any sound identified as a cough by both human observers will be considered a positive result for cough. TP will be defined as those sounds identified as a cough by Hyfe, and both human observers. Similarly, a sound identified as non-cough by both observers will be considered a negative. TN will be defined as those sounds not recorded as coughs by neither Hyfe, nor any human observer. Sounds identified as coughs by Hyfe, but not by both human observers will be considered FP, and those identified as non-cough by Hyfe, but not by both human observers will be classified as FN. Sounds for which no consensus is reached by both human observers will be excluded from the analysis. Time stamps from each individual sound will be used to identify them, and determine which ones were not picked up by Hyfe's detection algorithm.

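### In the real-life sub-study no rule says whose cough is counted, so the planned figures measure cough detection but cannot show that the count is the participant's own

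*Combined protocol and SAP*

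**What the plan says.** Section 4.1 (Validation of Hyfe's technical performance) describes a second sub-group of at least 24 people. They use the phone app and the Hyfe Air wearable together "for a period between 6 and 24 hours", "while they record themselves using a MP3 recorder connected to a lapel microphone". The recordings are then "manually reviewed by two specially trained healthcare providers to count the number of coughs recorded". This serves secondary objective 4, sensitivity and specificity in real life.

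Section 9.1 sets the scoring for secondary objectives 3 and 4:

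- Reference positive: "Any sound identified as a cough by both human observers will be considered a positive result for cough".
- True positive: "TP will be defined as those sounds identified as a cough by Hyfe, and both human observers".
- Matching: "Time stamps from each individual sound will be used to identify them".
- Sounds on which the two observers disagree are left out.

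Global design (section 4.1) says that the system "identifies human cough based on acoustic characteristics". Sections 2.1 and 6 describe a cough/non-cough classifier, and no section describes recognition of the phone's owner or the wearer. Participants given a study phone are told to "keep the study smartphone close to them for the period of monitoring", so the phone is nearby rather than worn.

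No section tells the reviewers to label, exclude or separately score a cough from another person.

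**The concern.** The clinical part of the study treats each logged cough as the participant's own. Section 7.2 uses the hourly cough rate. Section 9.1 relates that person's cough frequency to that person's VAS score, and reads before-after change as evidence on clinical evolution. Under Generation of annotated cough datasets (section 4.1), sounds are filed under the participant's diagnosis, and section 9.1 uses such records to train the disease classifier.

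Objective 4 is the only test in this plan of the devices outside a controlled room. If a housemate's or ward neighbour's cough reaches both the recorder and the phone, the stated rule scores it as a success. In the clinical cohort the same event would add to the wrong person's count. Section 5.1 requires no complaint of cough for objectives 3 and 4, so some wearers may cough little, and other people's coughs could then be a large share of what is heard.

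The phone and Hyfe Air may also differ on exactly this point, because one lies nearby and the other is worn. The planned figures cannot separate that difference from a difference in cough detection.

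**Working it through.** **The plan's own figure.** The documents give no figure for coughs from other people. The only number attached to this sub-study is the sample size that section 9.2 carries over from objective 3: 24 × 12 = 288 coughs, 90% power, sensitivity 95% versus 90%. A one-sample test at two-sided 5% (sidedness is not stated) gives 89.5% power by the exact binomial and 92.0% by the normal approximation. The stated 90% is therefore reproduced, and nothing below depends on it.

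**Where a bystander's cough goes under section 9.1**

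| Event | Scored as | Effect on planned figures |
|---|---|---|
| Both reviewers and Hyfe call it a cough | True positive | Wrong-person attribution is hidden |
| Both reviewers hear it, Hyfe does not log it | False negative | Sensitivity is lowered |
| Hyfe logs it, neither reviewer calls it a cough | False positive | PPV is lowered, so already penalised |
| Reviewers disagree | Excluded | None |

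**Illustration of size.** Inputs:

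- w = 100 wearer coughs (assumed).
- b = 5, 10 or 25 bystander coughs heard by both reviewers (assumed).
- s = 0.9634, the share of wearer coughs that Hyfe logs. This is a nominal value from section 6, which says that it covers only sounds the app had already detected.
- d, the share of bystander coughs that Hyfe logs: equal to s, or 0.30 (both assumed).
- No other false positives (assumed).

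Formulas:

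- Planned sensitivity = (ws + bd)/(w + b)
- Planned PPV = 100%, because every logged sound is a reference positive
- Wearer-level PPV = ws/(ws + bd)
- Count ratio, Hyfe to wearer = (ws + bd)/w

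When d = s, the sensitivity cancels and wearer-level PPV is w/(w + b): 100/105 = 95.2%, 100/110 = 90.9%, 100/125 = 80.0%. When d = 0.30, it is 96.34/(96.34 + 1.5) = 98.5%, 96.34/(96.34 + 3) = 97.0%, and 96.34/(96.34 + 7.5) = 92.8%.

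| b | d | Planned sensitivity | Planned PPV | Wearer-level PPV | Count ratio |
|---|---|---|---|---|---|
| 5 | 0.9634 | 96.3% | 100% | 95.2% | 1.01 |
| 10 | 0.9634 | 96.3% | 100% | 90.9% | 1.06 |
| 25 | 0.9634 | 96.3% | 100% | 80.0% | 1.20 |
| 5 | 0.30 | 93.2% | 100% | 98.5% | 0.98 |
| 10 | 0.30 | 90.3% | 100% | 97.0% | 0.99 |
| 25 | 0.30 | 83.1% | 100% | 92.8% | 1.04 |

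Wearer-level sensitivity is 96.3% in every row. In the lower half of the table the planned sensitivity falls below it, because bystander coughs that Hyfe correctly leaves out are scored as misses.

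**Comparing the two devices.** Assume 288 wearer coughs and 72 bystander coughs (20% of those heard), and that each device logs 90% of wearer coughs. Assume also that the phone logs 90% of bystander coughs and Hyfe Air 30%.

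- Phone: 259.2 + 64.8 = 324.0 logged. Planned sensitivity is 324.0/360 = 90%; wearer-level PPV is 259.2/324.0 = 80%.
- Hyfe Air: 259.2 + 21.6 = 280.8 logged. Planned sensitivity is 280.8/360 = 78%; wearer-level PPV is 259.2/280.8 = 92%.

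Under these assumptions the device that better isolates the wearer looks worse on sensitivity, and the planned PPV is 100% for both.

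**The case against.** The strongest reply is that the plan answers the question it sets. Objective 4 asks for sensitivity and specificity against human listeners. Section 6 explains why: the earlier data missed any cough the app never picked up, so continuous recordings are needed. That is a cough/non-cough question, section 9.1 addresses it, and section 9.2 calls the analysis exploratory. This stands. Whose cough was counted is an additional quantity, not an error in the stated one.

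Second, participants record themselves through a worn lapel microphone, and the reviewers are specially trained. A reader might infer from the silence that reviewers will ignore the source of a cough. The documents do not say that. They do not give the content of the training, and the microphone may well make other people's coughs faint, disputed or unheard. But neither feature is a scoring rule. The microphone is also what makes attribution practicable.

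Third, a reader might infer that reported accuracy is inflated across the board. The rules do not support that: only one of the four routes flatters the device, and one lowers its sensitivity. Nor would a difference between phone and Hyfe Air stay invisible. Their sensitivities or false-positive counts would differ, but the figures would not show why and could point the wrong way.

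**Conclusion.** The point holds as a gap in what objective 4 can support. The section 9.1 figures can stand as cough-detection accuracy, but not as evidence that a count or a stored sound belongs to the participant. The quiet-room sub-study (objective 3), with one participant at a time, is largely unaffected.

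The absence of an attribution rule is certain from the text. The size and net direction of its effect are not. Wearer-level PPV of 80% to 98% in the illustrations rests on assumed bystander numbers, assumed detection of bystander coughs and no other false positives. A reader might take 80% as an estimate. It only restates an assumed ratio of 100 to 25 with equal detection, and the same ratio with 30% bystander detection gives 93%.

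**What to change.** Before review starts, add to the objective 4 procedure that the same two reviewers label each cough as *participant*, *other person* or *cannot tell*, with disagreement on source treated as *cannot tell*. Then:

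- Keep the section 9.1 figures, described as cough-detection accuracy.
- For each device, add wearer-level sensitivity (reference: participant coughs only) and wearer-level PPV. A Hyfe detection of another person's cough is a wearer-level false positive; one that Hyfe leaves out is not a false negative.
- For each device, add the ratio of Hyfe count to wearer cough count.
- Repeat the wearer-level figures with all *cannot tell* coughs assigned to the participant, then all to others.
- Base any statement about patient monitoring on the wearer-level figures.

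The cost is one extra label in a review already planned, with no change in sample size. Review will be slightly slower, some coughs will be unattributable, and the wearer-level PPV is likely to look less favourable. Adding the label afterwards would mean listening again to 24 × 6 = 144 to 24 × 24 = 576 hours of audio.

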## **5. SELECTION OF STUDY SUBJECTS**

### ***5.1. Inclusion criteria***

All the patients should comply with the following criteria for inclusion:

For objectives 1 and 2:

1. Outpatient or inpatients at the Clínica Universidad de Navarra with a complaint of cough.
2. The patient or his/her legal representative, have given consent to participate in the study.

For objectives 3 and 4:

1. Being 18 years or older.
2. Providing consent for the specific the sub-study.

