At an individual level, continuous cough monitoring has also been long-considered a good proxy of response to treatment in patients with chronic pathologies. But the process still depends on either subjective report by patients, or manual counts of cough episodes recorded by specialized instruments. (Decalmer et al, 2007) We now intend to evaluate the efficacy of a mobile acoustic tool to monitor treatment progression and facilitate etiologic diagnosis in patients with chronic cough of unknown origin at the Clínica Universidad de Navarra.

Furthermore, these systems could also be refined to facilitate the identification of patterns associated to specific diseases. Similar strategies have been already used for the screening of asthma (Porter et al, 2019, Sharan et al, 2018), tuberculosis (Prahar et al, 2021) and COVID-19 (Laguarta, Huet, Subirana, 2020), but not in the context of chronic cough, whose clinical diagnosis remains particularly challenging. In this study, we will (i) evaluate the value of AI-enabled cough monitoring systems for screening, diagnosis, and management of respiratory diseases. We will also simultaneously (ii) collect data from patients with a known diagnosis to enrich existing, public disease-annotated cough datasets for the further training of cough-recognition AI systems, and (iii) assess the technical performance of available digital cough monitoring applications.

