## 9. STATISTICS

### ***9.1. Description of the statistical methods to be used, including the schedule of all the planned intermediate analyses***

For completion of the primary objective

To assess the accuracy of the cough surveillance system to detect cough patterns associated to specific diseases, we will use participants in which an etiologic diagnose is reached before completion of the study. We will search for digital footprints of singular detected cough events, and/or the pattern of cough in time for participants with a given diagnosis.

These records will be used to train a previously developed convolutional neural network to perform respiratory disease cough classification. We will initially use a random split-sample approach (70% derivation & 30% validation) to assess the performance of the newly generated cough classification tool (sensitivity, specificity, positive and negative predictive values, AUC). Performance will then be validated by retrospectively analyzing these participants' coughs with the newly trained AI-network.

The cough classification tool will be supplemented with patient-specific information to assess the incremental value of cough-based multi-variable prediction.

For secondary objective 1

The daily VAS score of participants will be compared to the cough frequency registered by the cough surveillance system. These data will be used to fit a linear regression model to compare self-reported VAS scores to daily cough frequency and calculate a correlation coefficient ( $r$ ). The

average weekly VAS score and cough frequency on week 1, will be compared to that at study withdrawal using a paired t-test, and represented using before-after plots. P values below 0.05 will be considered significant. A similar approach will be used to compare results of the LCQ at the beginning vs the end of the study. Before-after plots will be constructed to represent these differences. This approach is also expected to provide information on the system's capacity to reflect clinical evolution of participants (Primary objective).

For completion of secondary objective 2

Cough registries of participants with an etiologic diagnosis of respiratory disease will be included in annotated datasets. There are no specific statistical analysis required for completion of this objective.

For completion of secondary objectives 3 and 4

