## **9.2. Sample size calculations**

### *Primary objective*

For the primary objective, sample size calculations are complicated due to the variability of cough frequency between different patients with different conditions. To evaluate the system's capacity to detect and classify coughs based on their etiology, we will create and prospectively

increase a split-sample (derivation / validation) dataset and test performance until it plateaus (see data analysis). Based on previous digital cough diagnostic studies performed by the co-investigators, we anticipate needing 15,500 individual cough data points and 200 cough time series by groups for every individual diagnosis. This number of coughs might be rapidly reached by participants diagnosed with a cause of chronic cough but will likely take substantial time for other acute conditions. Thus, the suggested duration of 5 years.

To evaluate the capacity of the system to reflect changes in cough frequency associated to clinical evolution, sample size calculations are more straightforward and detailed below.

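### The stated question about the causes of chronic cough has no matching analysis: section 9.1 evaluates the classifier over all diagnoses and describes none within chronic cough

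*Combined protocol and SAP*

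**What the plan says.** - **Question.** Section 3 lists two research questions. The second is "can acoustic cough patterns facilitate the etiologic diagnosis of patients with chronic cough". Section 2 gives the reason: similar tools have been tried for several diseases, "but not in the context of chronic cough, whose clinical diagnosis remains particularly challenging".
- **Definition.** Section 2.2 defines chronic cough by duration: "Typically considered to be any cough that lasts for 8 weeks or longer".
- **Primary objective.** It is wider than that question: "To evaluate the value of AI-enabled cough monitoring systems for screening, diagnosis, and management of respiratory diseases in clinical practice".
- **Entry.** For objectives 1 and 2, section 5.1 takes "Outpatient or inpatients at the Clínica Universidad de Navarra with a complaint of cough", given consent. There is no limit on duration.
- **Classifier analysis set.** In section 9.1, "we will use participants in which an etiologic diagnose is reached before completion of the study". Inputs may be single cough events, the pattern of cough over time, or both. Sensitivity, specificity, predictive values and AUC come from a random 70/30 split. Patient-specific information is then added to assess incremental value.
- **Acute disease in that set.** Section 9.2 states "we anticipate needing 15,500 individual cough data points and 200 cough time series by groups for every individual diagnosis" and says that reaching the cough count "will likely take substantial time for other acute conditions".

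Section 9.1 does not say which participants serve as comparators for a given diagnosis. It describes neither a chronic-only analysis nor stratification by cough duration.

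**The concern.** Whether a cough has lasted 8 weeks is something a clinician learns by asking. The hard task, by the protocol's own account, is to tell one cause of chronic cough from another. If a chronic disease is compared with a mixture of other chronic causes and acute illness, part of the reported accuracy can come from separating acute from chronic. That part says nothing about question (ii).

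There are plausible routes for it. The pattern of cough over time is a permitted input. Under the monitoring-period text in section 4.1, inpatients are followed to discharge and outpatients initially for one month, so the length of a series may itself carry information on setting and acuity.

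Two things are at stake. A reader could take an all-diagnosis AUC as the answer for chronic cough when it is not. The figure would also move with the acute/chronic mix recruited over up to five years, even if the tool's ability within chronic cough stayed the same.

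**Working it through.** **The plan's own figure.** The only figure tied to this analysis is 15,500 coughs and 200 time series per diagnosis. Section 9.2 rests it on the co-investigators' earlier studies and gives no target accuracy, alpha, power or formula, so it cannot be reproduced. The point does not depend on it.

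**Step 1: AUC against mixed comparators.** For one chronic diagnosis against the rest, let w be the acute share of the comparators. The AUC is the chance that a random target case scores above a random comparator, so

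AUC(mixed) = (1 − w) × AUC(vs chronic) + w × AUC(vs acute).

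The excess over the chronic-only figure is w × [AUC(vs acute) − AUC(vs chronic)]. It is positive whenever acute comparators are easier to separate. At a fixed threshold, specificity is a weighted mean in the same way.

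**Step 2: illustration.** The documents give neither w nor the component AUCs, so all three are assumptions. AUC(vs acute) is set at 0.95.

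| Acute share w | AUC(vs chronic) = 0.65 | AUC(vs chronic) = 0.50 |
|---|---|---|
| 10% | 0.585 + 0.095 = 0.680 | 0.450 + 0.095 = 0.545 |
| 25% | 0.4875 + 0.2375 = 0.725 | 0.375 + 0.2375 = 0.613 |
| 50% | 0.325 + 0.475 = 0.800 | 0.250 + 0.475 = 0.725 |
| 75% | 0.1625 + 0.7125 = 0.875 | 0.125 + 0.7125 = 0.838 |

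**Step 3: limiting case.** Take a score that carries no etiologic information among chronic causes and separates acute from chronic with AUC A. Then AUC(mixed) = 0.5 + w × (A − 0.5). With w = 0.5 this gives 0.65 for A = 0.8, 0.70 for A = 0.9 and 0.75 for A = 1.0. Restricted to chronic cough it is 0.50 in every case.

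A share of 50% would arise with, for example, four chronic and three acute groups of equal size: three of the six comparator groups are acute. If 200 series per diagnosis are split 70/30, 0.30 × 200 = 60 fall in validation. Simulating 60 target, 180 other chronic and 180 acute series 2,000 times with A = 1.0 gave a mean mixed AUC of 0.750 (95% of runs 0.709 to 0.791). The mean chronic-only AUC was 0.500 (0.418 to 0.582).

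**Step 4: precision of a chronic-only figure.** The Hanley-McNeil standard error at AUC 0.50, with 60 target series, is:

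- against 60 chronic comparators: √[(0.25 + 118 × 0.0833)/3,600] = 0.053, a 95% half-width of 1.96 × 0.053 = 0.104;
- against 180: √[(0.25 + 238 × 0.0833)/10,800] = 0.043, a half-width of 0.085.

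These treat the series as independent, one per participant.

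**The case against.** **Broad entry is not an error.** A reader might infer that section 5.1 should admit only chronic cough. The documents do not support that. The primary objective covers respiratory diseases in general, and section 2.2 includes patients with an existing respiratory diagnosis. This stands, and it places the gap in section 9.1.

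**Pooling is an inference.** No section says that one AUC is computed over all diagnoses. Section 9.1 speaks of specific diseases, and section 9.2 sizes each diagnosis separately. This stands as a limit on the wording. But group sizes do not define comparators, and no separate chronic analysis is described, so none is prespecified.

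**The mechanism is not certain.** A reader might infer that acute cough resolves within the monitoring month and so gives itself away by its course. The documents do not say so. Inpatients leave monitoring at discharge, chronic cough may fall under treatment, and a classifier built on single short cough sounds does not see the time course. Nor do the documents say that the acute comparators were never in clinical doubt. Only a conditional statement is justified.

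**The acute share may be low.** Section 9.2 expects chronic-cough data quickly and acute data slowly. At 10% acute, the excess in the first illustration is only 0.03.

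**The incremental-value step helps in part.** It bears on what the history already gives. But it names neither cough duration nor a history-only model, and it would not by itself show accuracy among chronic causes.

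**Conclusion.** The point holds as a gap in the analysis plan. Question (ii) asks about causes of chronic cough. Section 9.1 evaluates the classifier over all diagnosed participants, acute conditions expected among them, and describes no analysis that answers the question. If acute comparators are easier to separate, the all-diagnosis accuracy can exceed the accuracy among chronic causes.

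With assumed AUCs of 0.65 and 0.95, the excess runs from 0.03 at 10% acute comparators to 0.225 at 75%. These values are illustrations; only the direction follows from the algebra, and only under the stated condition.

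A reader might go further and conclude that the reported accuracy will be overstated. The documents do not support that: they give neither the case mix nor the relative difficulty of the comparisons. For the primary objective, an all-diagnosis figure is a legitimate result.

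**What to change.** 1. Leave the entry criteria in section 5.1 unchanged.
2. Make sure the physician's medical questionnaire (section 7.1.1) captures cough duration at enrolment. The form is not in the documents, so it may already do so. Duration is hard to recover reliably later.
3. In section 9.1, state that question (ii) is answered by sensitivity, specificity and AUC among validation participants whose cough had lasted 8 weeks or longer at enrolment, using only other chronic-cough participants as comparators. Report this alongside the all-diagnosis figure, which serves the primary objective and need not be demoted.
4. In the incremental-value step, define a history-only base model that includes cough duration, and report what the cough data add to it.

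The cost is at most one form item and some wording in section 9.1. Nobody is excluded. The chronic-cough figure will rest on fewer participants, with wider intervals (a half-width of about 0.085 to 0.104 in the cases worked above), and the AUC will probably be less favourable.
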